# 4.0 Resources and Personnel

Research procedures will be conducted at VA Puget Sound, Seattle Division. Study personnel as listed on the Institutional Review Board (IRB) and Research and Development Committee (R&DC) applications will have access to protected health information, will be involved in recruiting participants, will obtain consent, will conduct study interviews, and will administer study instruments. Generally, the staff includes Clinicians, Raters, Psychometrists, Study Coordinator(s), and Research Assistant(s) as described below.

#### **Description of Study Personnel:**

Study Clinicians: will perform safety assessments and examinations, make decisions regarding the dose titration schedule for individual participants, and make any necessary unscheduled dose changes. The Study Clinician will be a physician, physician assistant, or nurse practitioner with experience conducting clinical research in Veterans with TBI and with PTSD.

Study Raters: will administer all interview-based assessments. Raters will be master's level social workers or other study professionals who have extensive experience in performing these assessments in this study population.

Psychometrists(s) and/or Neuropsychologists: will administer all neuropsychological testing (as described in the study procedures section below). Psychometrists will be experienced and will have been trained by a neuropsychologist.

Study Coordinator(s) and Research Assistant(s): will be responsible for scheduling visits, conducting the portions of study visits that do not require clinicians, maintaining case report forms (CRFs), preparing reports for the IRB and subcommittees, and assisting the data manager.

Data Management: Database design, any required computer programming, and maintenance of computer hardware and software will be performed by the Data Management team. Initial and second data entry will be performed on a weekly basis by a study Research Assistant under the supervision of the Database Manager. The Database Manager will generate weekly reports of data discrepancies. The study Research Assistant under the supervision of the Study Coordinator and Data Manager will be responsible for rectifying data entry errors on a weekly basis.

Database maintenance includes nightly backup of servers and storage of backups at a safe offsite location. Only personnel having the correct user name, password, and signing on from a computer with the appropriate IP address will have access.

# 5.0 Study Procedures

Overview: We are proposing an initial, biomarker-based proof-of-concept pilot randomized clinical trial (RCT) of prazosin as a pharmacologic intervention to ameliorate PTSD and/or mild to moderate TBI as a risk factor for neurodegenerative dementia in Veterans. There will be two phases. In phase I, participants will all receive open-label prazosin. In phase II, participants will be randomized to double-blind prazosin or placebo. In each case, the study drug will be maintained for 5 weeks once full dose is reached. The first 5-8 weeks will be a titration period,

PTSD/TBI Glymphatic Protocol Version 3	VA Puget Sound IRB Protocol Template Version: 2/2015	Page 11 of 45
Revised 11/02/2018		6.2

where the dose of prazosin or placebo will be increased at regular intervals to a maximum dose of 25 mg in divided doses (see section 5.5 below for detailed description of dose titration). All procedures for this study are research procedures; none are standard of care.

Study Population: Participants will be Veterans from any conflict with a history of mild or moderate TBI, plus Veterans from any conflict with a current diagnosis of PTSD. Persons of all races, ethnicities, and genders are eligible to participate. Some participants may be VA employees. However, we are not targeting employees as a study population. Any VA employee will complete study visits on their off-duty time. Based on previous experience we expect a screen-failure and dropout rate of 30% each, requiring for phase I 29 participants to be screened in order to obtain an enrollment of 22, and requiring for phase II 120 participants to be screened in order to obtain an enrollment of 90 participants with at least 60 completers.

**Procedures:** Participants will undergo a lumbar puncture (LP) and will have blood samples collected prior to initiation of study drug and following 5 weeks at maximal dose of study drug. Blood collection for DNA analysis will also be done at the time of the first LP. Symptom assessments, neurocognitive testing, and quantitative and qualitative biologic measures likely to have predictive value for identifying individual variations in efficacy, including data on autonomic functioning and sleep, will also be collected both at baseline and at the time of completion.

Samples will be used for measurement of CSF biomarkers (total tau, p-tau181, Aβ42, F2-isoprostanes, brain-derived neurotrophic factor [BDNF], neuropeptide Y [NPY], corticotropin-releasing factor [CRF], hypocretin, nerve growth factor [NGF], Cholecystokinin [CCK], dynorphin, a cytokine panel, catecholamines [norepinephrine, epinephrine, and dopamine], indoleamines [serotonin] and their precursors and metabolites), serum and plasma biomarkers (fasting lipids, C-reactive protein [CRP], adrenocorticotropic hormone [ACTH], cortisol, total testosterone, insulin-like growth factor-1 (IGF-1), and catecholamines), RNA, microRNAs, and proteomics.

Proteomics, similar to genomics, is an unbiased method that simultaneously assesses thousands of proteins. There are several CSF biomarkers that reflect particular facets of neurodegeneration. Conducting a large-scale survey of potential CSF biomarkers will allow us to define a panel of biomarkers that may discriminate treatment effects and provide insight into as yet unknown mechanisms of action.

We will be studying the following genes: APOE, MAPT, AQP4, LRP-1, SUCLG2, GRIN2B, ADRA1A, NCAM, CYP19A1, TOMM40, CALHM1, MAO-A and COMT (see below for more detailed discussion of each gene's connection to the study); overall, each gene has been implicated in the mechanism or regulation of glymphatic flow, the progression of AD, the regulation of biomarkers of AD in CSF, and/or the metabolism of NA.

At the conclusion of the study, participants who have obtained relief of symptoms they may be experiencing during the study and who are interested in continuing on the medication will be provided with appropriate referrals to providers to prescribe prazosin for clinical care purposes, and will be provided with a bridging supply of the medication at the dose on which they had been stabilized.

Investigational Drug: This study will be conducted using the drug, prazosin, which has been approved by the FDA for treatment of hypertension but is being used off-label for investigational

PTSD/TBI Glymphatic Protocol Version 3	VA Puget Sound IRB Protocol Template Version: 2/2015	Page 12 of 45
Revised 11/02/2018		1

purposes in this study. Prazosin and indistinguishable placebo will be obtained. All study medications will be shipped to the investigational pharmacist at VA Puget Sound. Study drug may be stored at room temperature. Unused drug will be disposed of by the investigational pharmacist once notification has been made by the PI that the study has been completed.

Pursuant to 21 CFR 312.2(b)(1), the clinical investigation of a marketed drug or biologic does not require submission of an IND if all six of the following conditions are met:

- (i) it is not intended to be reported to FDA in support of a new indication for use or to support any other significant change in the labeling for the drug;
- (ii) it is not intended to support a significant change in the advertising for the product;
- (iii) it does not involve a route of administration or dosage level, use in a subject population, or other factor that significantly increases the risks (or decreases the acceptability of the risks) associated with the use of the drug product;
- (iv) it is conducted in compliance with the requirements for IRB review and informed consent [21 CFR parts 56 and 50, respectively];
- (v) it is conducted in compliance with the requirements concerning the promotion and sale of drugs [21 CFR 312.7]; and
- (vi) it does not intend to invoke 21 CFR 50.24 (Exception From Informed Consent Requirements for Emergency Research).

We do not intend to use the results of this research in support of a new indication for prazosin, nor do we intend to support significant change in advertising for prazosin. The route of administration, dosage level, and subject population are all the same as in general clinical practice, and do not increase the risks usually associated with prazosin. Thus, we have satisfied requirements i., ii., and iii. Requirement iv. is satisfied through the approval of this study by the appropriate Institutional Review Boards, and requirement v. is satisfied in that we are not promising any benefit from the use of prazosin in this study.

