Safety monitoring is based on long-term clinical experience with prazosin. Prazosin was first introduced in 1976 under the trade name Minipress (Pfizer) for clinical management of hypertension, and later became widely prescribed for urinary outflow obstruction secondary to benign prostatic hypertrophy (BPH). It has been safely prescribed to large numbers of middleaged and older people over the past 35 years. The following information regarding the side effect profile and safety record or prazosin is a synopsis from the Minipress package insert: "The most important adverse effect to be considered when prescribing prazosin is a "first dose effect" manifested by syncope with sudden loss of consciousness believed to be due to postural hypotension in approximately 1% of patients given an initial dose of 2 mg or greater. This rare adverse effect is self-limiting and in most cases does not recur after the initial period of therapy or during subsequent dose titration. However, patients should always be started on 1 mg of prazosin. In clinical trials of prazosin, most frequent adverse reactions were dizziness (10%), HAs (8%), drowsiness (8%), lack of energy (7%), weakness (7%), palpitations (5%), and nausea (5%). Less frequent adverse reactions (1-4%) were: vomiting, diarrhea, constipation, edema, orthostatic hypotension, dyspnea, syncope, vertigo, depression, nervousness, rash, urinary frequency, and nasal congestion. Fewer than 1% of patients have reported the following (causal reactions sometimes not established): abdominal discomfort or pain, tachycardia, paresthesias, hallucinations, pruritus, incontinence, impotence, and priapism..."

Through extensive experience of our group, including open-label clinical studies, placebo-

PTSD/TBI Glymphatic Protocol Version 3	VA Puget Sound IRB Protocol Template Version: 2/2015	Page 17 of 45
Revised 11/02/2018		

controlled trials, and clinical application, prazosin has demonstrated a favorable safety profile. It has been estimated that over 70,000 Veterans nationwide are being treated with prazosin for PTSD. Approximately 5% of those treated with prazosin have discontinued it secondary to subjectively unpleasant side effects, most commonly transient orthostatic dizziness, nasal congestion, or exercise-induced tachycardia.

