For participants completing the entire trial, the blind will be broken by a Study Clinician at the end of the study (except if they are participating in a simultaneous prazosin study: in those cases, the blind will be broken when the longer study period ends). Maintaining the blind until all participants have completed the protocol and the database has been locked would be ideal; however, previous studies have shown that optimal safety and follow-up patient care argues in favor of breaking the blind for each person when they complete the trial. All participants will be given the option of treatment with open-label prazosin after study completion (an important condition for recruitment, given that prazosin is clinically available). The appropriate and safe method for initiating open-label prazosin differs depending on whether the participant had been randomized to prazosin or placebo. For those randomized to prazosin and wishing to continue, subsequent open-label prazosin should be kept at the maximum achieved dose, and may be titrated further upward, if additional clinical benefit might be obtained. On the other hand, participants randomized to placebo will require titration to effect, as per the study titration schedule, initiated at a low dose (1 mg) to avoid the risk of first-dose hypotension.

Once the blind has been broken for a participant, they will be provided a written report describing the information from their ambulatory blood pressure and actigraphic monitoring data. These will be provided as a standardized report, generated by the analysis software for these systems. The participant will be informed that these are not being conducted as medical tests but rather as experimental data collection, and the data is being provided for their interest, rather than as the result of a medical test. We will be able to discuss the reports with the participants and refer them to their primary care provider if follow-up is warranted.

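### The bridging-supply sentence in section 5.0 does not distinguish treatment arm although section 5.6 makes the start of open-label prazosin arm-specific, and nothing puts unblinding before dispensing

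*Combined protocol and SAP*

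**What the plan says.** Two places in the protocol govern what a participant receives on leaving the study.

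- **Section 5.0, Procedures.** The sentence covers "participants who have obtained relief of symptoms they may be experiencing during the study and who are interested in continuing on the medication". They are referred to a prescriber, and each "will be provided with a bridging supply of the medication at the dose on which they had been stabilized". Treatment arm is not mentioned, and there is no cross-reference to section 5.6.
- **Section 5.6, Withdrawal of Subjects.** A Study Clinician unblinds each participant who completes the whole trial when that person's participation ends. One group is treated differently: "except if they are participating in a simultaneous prazosin study: in those cases, the blind will be broken when the longer study period ends". Further on, the section says: "All participants will be given the option of treatment with open-label prazosin after study completion". The safe starting method is said to depend on arm. Prazosin participants stay at the highest dose they achieved, whereas "participants randomized to placebo will require titration to effect, as per the study titration schedule, initiated at a low dose (1 mg"), the stated purpose being to avoid first-dose hypotension.

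Other sections bear on how the two are read:

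- Section 5.0 (Overview) and section 5.4 (Study Treatment Period): prazosin and placebo are both stepped up to a highest tolerated dose, which is then held.
- Section 5.5 (Participant Randomization): sealed envelopes serve to break the blind in an emergency and after the termination assessments, with a pointer to section 5.7. The investigational pharmacist has access to the codes. The contents list ends section 5 at 5.6.
- Section 5.4 (Schedule of Study Visits): drug dispensing or collection is marked at visit 12, the last visit.

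**The concern.** A placebo participant in phase II is titrated and stabilized on a nominal dose in the same way as a prazosin participant, and may report relief. Nothing in the section 5.0 sentence excludes that person. Applied literally, it would supply active drug at the nominal stable dose to someone who has taken no prazosin in the study. Section 5.6 treats that situation as needing a different start.

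The risk is one the protocol itself stresses. Its safety text in section 5.0 reports syncope at the first dose in "approximately 1% of patients given an initial dose of 2 mg or greater". Section 5.4 therefore surrounds the first doses with in-bed dosing, a call the day after the first dose, and a visit at each later dose increase. None of these has a scheduled counterpart after visit 12. The referral to a prescriber does follow, but the bridging supply exists to cover the time before that prescriber takes over.

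The stake is participant safety at dispensing. The point does not bear on the power calculation or on the analysis of the biomarkers.

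**Working it through.** No planned statistical figure is involved. The check sets the texts side by side for each kind of participant, with simple counts.

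**Does a placebo participant have a stabilized dose?** Yes, nominally (sections 5.0 and 5.4). At full titration the last row of the section 5.4 table is 5 mg morning, 5 mg afternoon and 15 mg bedtime: 5 + 5 + 15 = 25 mg, matching the maximum in section 5.0. A first dose from a supply at that level would be 5 mg or 15 mg, depending on the time of day. The ratio 15 / 1 = 15 to the 1 mg start is therefore an upper case, since participants may stabilize lower.

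**Who could be concerned?**

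- Phase I: all receive open-label prazosin, so placebo participants = 0.
- Phase II, 2:1 allocation, 60 planned completers (section 5.5): 60 × 1/3 = 20 on placebo.
- Phase II, 90 planned enrolled: if split 2:1, 90 × 1/3 = 30 on placebo, so 30 − 20 = 10 placebo participants would leave early.
- How many placebo completers would report relief and ask to continue is not given. The range is 0 to 20.

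**Do sections 5.0 and 5.6 agree?**

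| Participant | Section 5.0 bridging sentence | Section 5.6 | Result |
|---|---|---|---|
| Completer, revealed as prazosin | Stabilized dose | Highest achieved dose | Agree |
| Completer, revealed as placebo | Stabilized dose, if read literally | Titration from 1 mg | Disagree |
| Dual-enrolled, still blinded | Stabilized dose, if read literally | Arm unknown, so the arm-specific rule cannot be applied | Not resolved |
| Early leaver | Not stated whether it applies | Unblinding sentence limited to full completers | Not resolved |

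**Is the order of events fixed?** Section 5.6 places unblinding at the end of the study, and section 5.0 places the bridging supply at its conclusion. Neither says that the first must precede the second. The only other guidance, in section 5.5, points to a section that is not in the contents list.

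**How wide is the dual-enrolment gap?** Section 5.4 (item 4b of the concurrent-study rules) puts this study's end-of-study procedures after the concurrent study's treatment period. A participant is therefore still blinded at that point only if the other study continues beyond its own treatment period. The documents do not say whether it does.

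**The case against.** The strongest reply is that section 5.6 already deals with this hazard. It accepts unblinding each completer individually, which it admits is less than ideal, precisely so that the starting method can match the arm. The pharmacist, to whom all study drug is shipped, has the codes. The section 5.0 sentence speaks of continuing a medication at a stabilized dose, which fits prazosin recipients naturally. Read that way it agrees with section 5.6, and section 5.0 is an overview while section 5.6 is the specific procedure. The dual-enrolment case is narrow, and for some of those participants the drug is given under another protocol that is not available here.

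Most of this stands. A reader might infer that every placebo participant who wants to continue will be handed the full titrated dose, or that the two rules can never be applied together. The documents do not support either reading. Section 5.0 also requires symptom relief and provides a referral. An ordinary completer's assignment is to be revealed at the end of the study. A full-dose first exposure would need staff to act on section 5.0 without regard to section 5.6. No text says that a still-blinded participant is given a bridging supply.

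What the reply does not supply is the missing order of steps, the missing arm qualifier, or a rule for participants outside the main unblinding sentence. The envelope text in section 5.5 may have been meant to cover early leavers, but its pointer leads nowhere.

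**Conclusion.** The point holds as an inconsistency between sections 5.0 and 5.6 on first-dose safety. It permits an error; it does not plan one. For ordinary phase II completers, end-of-study unblinding and the pharmacist's access to the codes largely prevent the error. The remaining exposure lies in the unstated order of unblinding and dispensing, the delayed unblinding of dual-enrolled participants, and the silence on early leavers.

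Phase I is not affected. In phase II the number of placebo completers concerned lies between 0 and the 20 planned, and the upper end is simply the size of the arm. It is not an estimate of how often the wrong supply would be given. Two limits apply. The documents give no syncope rate for a first dose of 5 mg or 15 mg, so no expected number of events can be calculated. They also do not say whether participants randomized before the open-label phase was added count towards the 60, so the 20 rests on the planned phase II numbers only. No view is taken on which dose or starting rule is right.

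**What to change.** Reconcile the bridging-supply sentence in section 5.0 with section 5.6:

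1. Have section 5.0 refer to the arm-specific rule in section 5.6.
2. State the order of unblinding and dispensing, and who confirms the assignment.
3. State what applies to each of four groups: revealed as prazosin, revealed as placebo, still blinded because of a concurrent study, and leaving early.
4. Correct the pointer to section 5.7 in section 5.5.
5. Make the pharmacy instructions say the same.

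The clinical content of each rule is for the study clinicians. The cost is protocol and pharmacy wording, with no added visits or participants. It is best done before phase II participants reach visit 12.

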#### Foreseeable Risks:

Venipuncture and i.v. placement: May cause transient pain and bruising at the site of the needle stick. Infrequently, participants may experience fainting or dizziness and there is also a slight risk of infection at the site of the needle stick.

Genetic Studies: We will be studying the following genes: APOE, MAPT, AQP4, LRP-1, SUCLG2, GRIN2B, ADRA1A, NCAM, CYP19A1, TOMM40, CALHM1, MAO-A, COMT, CRHR1, SLC6A2, and ADRA2A. APOE and MAPT have been associated with increased risk and/or progression of various neurological disorders as well as brain injury. The APOE-4 allele has been implicated as a risk factor for development of AD in later life. However, APOE type should not be considered a genetic test for AD since the results will not conclusively determine whether a person or any of his/her relatives have or might develop AD. MAPT codes for the microtubule associated protein tau, whose transcript gives rise to a variety of splicing variants including the

<sup>1 Promotion of an investigational new drug. A sponsor or investigator, or any person acting on behalf of a sponsor or investigator, shall not represent in a promotional context that an investigational new drug is safe or effective for the purposes for which it is under investigation or otherwise promote the drug. This provision is not intended to restrict the full exchange of scientific information concerning the drug, including dissemination of scientific findings in scientific or lay media. Rather, its intent is to restrict promotional claims of safety or effectiveness of the drug for a use for which it is under investigation and to preclude commercialization of the drug before it is approved for commercial distribution.

tau protein that accumulates in multiple neurodegenerative diseases. The rest of the genes we are studying have even less clear clinical interpretation at present, and are considered entirely experimental / investigational in their interpretation.

Participants are informed that currently, the results of these genetic tests do not have any clinical relevance and will be used for research purposes only. Participants will not be informed of their genotyping results. Participants will be told that if they wish to know their *APOE* genotype, that they can have the testing done at a commercial lab at their own expense.

The Genetic Nondiscrimination Act of 2008 protects participants against risks to employability and access to health insurance due to participation in genetic studies. However, it is theoretically possible that participation in genetics studies may jeopardize access to life insurance, disability insurance, or long-term care insurance if involvement and/or results of the study become part of the medical record. Procedures to minimize such risk are described below.

Clinical Assessment and Neuropsychological Testing, including pupillometry: Risks due to clinical assessment procedures are modest. Participants may experience stress similar to that of a standard clinical evaluation for memory complaints or dementia. Participants may also receive information that they are cognitively impaired. Such information may be distressing to a participant. The neuropsychological assessment battery may cause fatigue and/or unpleasant affective states due to the large number of individual tests. For the pupillometry portion of the neurocognitive testing, participants will be expected to keep their head relatively still, with their chin resting on a chin-rest platform, for approximately 15 minutes, which can be mildly uncomfortable. Some of the clinician and self-administered assessment instruments may cause participants to focus their attention on traumatic war-zone related experiences and as a result may produce transient subjective distress. However, these war-zone experiences are routinely assessed and discussed as part of standard clinical care.

Actigraphy, Ambulatory blood pressure (BP) and heart rate (HR) measurement: Wearing an Actiwatch for actigraphy measurements can be uncomfortable. Wearing the ambulatory BP monitor can be uncomfortable, and the intermittent inflation of the cuff can be both uncomfortable and can cause anxiety by occurring at unexpected times.

Wearing the ambulatory HR monitor can be uncomfortable as well. Some people find that the leads irritate their skin over time. The leads can also cause discomfort at the time of removal if they are placed over chest hair.

Confidentiality: We will take all due care so that responses to questionnaires are not commingled with patient medical records. However, because we are administering medications which may have interactions with other medications, it will be documented in the participant's medical record that they may be taking prazosin. We plan on obtaining a Federal Certificate of Confidentiality (CoC) to protect information collected. The study team will have access to VA Computerized Patient Record System (CPRS) records from initial consent until 30 days beyond the end of study participation. Results of clinically indicated screening labs will be placed in the participant's CPRS record and will be available to any of the participant's other VA health care providers or any health care providers to whom a participant releases his/her medical records.

Prazosin: There are no known absolute contraindications to prazosin. In clinical trials of prazosin, the most frequent adverse reactions were: dizziness (10%), drowsiness (8%), headache (8%), lack of energy (7%), weakness (7%), palpitations (7%), and, nausea (5%). Less frequent

PTSD/TBI Glymphatic Protocol Version 3	VA Puget Sound IRB Protocol Template Version: 2/2015
Revised 11/02/2018	

adverse reactions (1-4%) reported in clinical trials were: vomiting, diarrhea, constipation, edema, orthostatic hypotension, dyspnea, syncope, vertigo, depression, nervousness, rash, urinary frequency, blurred vision, reddened sclera, epistaxis, dry mouth, and nasal congestion. Fewer than 1% of patients have reported the following (causal relations sometimes not established): abdominal discomfort or pain, liver function abnormalities, pancreatitis, tachycardia, paresthesias, hallucinations, pruritus, alopecia, lichen planus, incontinence, impotence, priapism, tinnitus, diaphoresis, fever, positive ANA titer, and arthralgia.

Prazosin may cause syncope. In most cases this is believed to be due to excessive postural hypotension although occasionally the syncopal episode has been preceded by severe tachycardia with heart rates of 120-180 beats per minute. Syncopal episodes have usually occurred within 30-90 minutes of the initial dose. The incidence of the syncopal episodes is 1% if the initial dose is 2 mg or more. Clinical trials suggest that syncopal episodes can be minimized by starting with a dose of 1 mg and slowly titrating up to the final dose, as we are doing in this study.

